#### 10.7.3. Treatment Delays

EZN-2279 or Adagen® will be administered weekly ± 1 day. The PI, after upon consultation with Leadiant Biosciences and Lead PI, may elect to delay or withhold a dose if the clinical condition of the patient warrants such action. The PI, Leadiant Biosciences, and Lead PI must agree upon all modifications in the dosing regimen for each patient before any changes are instituted.

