### 11.2.3. Adagen® Pharmacokinetics

#### 11.2.3.1. Day 1

Day 1 is the day of the first administration of Adagen® on study. Prior to administration of Adagen® the following baseline procedures will be performed:

- Update medical history
- Physical examination
- Height and weight for growth assessment

- Performance status
- Vital Signs
- Safety Lab
  - Hematology
  - Chemistry
  - Urinalysis
- Other labs – blood samples will be obtained 15 to 30 minutes prior to dosing for:
  - dAXP
  - Trough ADA activity
  - B-, T-, and NK-lymphocyte subset analysis
  - Quantitative immunoglobulins
  - Adagen® antibody titers (i.e., neutralizing and binding antibodies) and anti-PEG antibodies
- Assessment of concomitant medications and procedures since last study visit

Following completion of the above procedures, the patient will receive Adagen® at his/her current weekly dose administered as a single weekly injection.

#### 11.2.3.2. Days 2 through 8

Blood samples for ADA activity will be obtained at 24, 48, 72, 96, 120, 144, and 168 hours following Day 1 PK dose. All blood samples will be obtained  $\pm$  4 hours of the scheduled collection time. Note: the 168 hour post-dose sample will be obtained immediately prior to the initial dose of EZN-2279.

For patients < 10 years of age, PK sampling will be limited to trough samples and at 48 hours post dose for monitoring of ADA activity and  $C_{max}$  timepoint.

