### 11.3. EZN-2279 Study Treatment Period

#### 11.3.1. Day 1 (Week T-1)

Prior to administration of EZN-2279 the following procedures will be performed:

- Physical examination
- Height and weight for growth assessment
- Performance status
- Vital Signs
- Safety Lab
  - Hematology
  - Chemistry
  - Urinalysis
- Other labs – blood samples will be obtained 15 to 30 minutes prior to dosing for:
  - dAXP
  - Trough ADA activity (168 hours following Day 1 Adagen® PK dose)
  - B-, T-, and NK-lymphocyte subset analysis
  - Quantitative immunoglobulins
  - EZN-2279 and Adagen® antibody titers (neutralizing and binding antibodies) and anti-PEG antibodies
- Adverse event assessment
- Assessment of infectious complications and hospitalizations
- Assessment of concomitant medications and procedures since last study visit

Following completion of the above procedures, the patient will receive EZN-2279. The equivalent dose of EZN-2279 will be calculated as described in Sections 7.2.1 and 10.7.1.

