## 12. ADVERSE EVENTS

### 12.1. Assessment Period

The AE reporting period for this study begins with the first lead-in dose of Adagen® and ends 30 days after the final dose of EZN-2279 (or, for patients who are withdrawn before switching treatment to EZN-2279, 30 days after the final dose of Adagen®).

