7.8 Concomitant Medications

All concomitant medications will be coded using the WHO Drug, Version 2013Q1 or most recent version prior to database lock. The frequency of concomitant medications will be summarized using descriptive statistics by therapeutic class and preferred term. Patients are counted only once in each therapeutic class category, and only once in each preferred term category.

There will be two concomitant medication summaries provided: all medications taken while the patient takes Adagen[®] study drug and all medications taken while the patient takes EZN-2279.

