10.4 Screening, Baseline and Study Weeks

No windowing schemes will be applied to the data. For by-visit summaries, if there are multiple assessments at a post baseline visit then the last non-missing assessment at that visit will be used for the summary. This includes assessments at the scheduled and unscheduled visits. For Patients who withdraw from the study, data at the early termination visit will be excluded from the by-visit summaries but will be included in the endpoint summaries.

Screening is defined as the last measurement for a variable before the initial dose of Adagen[®] study drug. With the exception of adverse events and medications, assessments collected at the screening visit are associated with the screening period because Adagen[®]

is not administered until all procedures are complete. Adverse events and medications starting on the day of the first dose of Adagen[®] are associated with Adagen[®] treatment.

Baseline is defined as the last measurement for a variable before the initial dose of EZN-2279 study drug, and is only used as the starting point for efficacy endpoints. With the exception of adverse events and concomitant medications, assessments collected at EZN-2279 Day-1 (Week T-1) are associated with Adagen[®] treatment because EZN-2279 is not administered until all procedures are complete. Adverse events and concomitant medications starting on the day of the first dose of EZN-2279 are associated with EZN-2279 treatment.

With regard to screening and baseline determination, assessments falling exactly on the date of the first dose of each study medication will be considered pre-dosing for that medication with the exception of adverse events and concomitant medications, which will be associated with the respective study drug.

Missing data will not be imputed.

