10.6 Safety Data Handling

For the purposes of AE reporting, three time periods will be defined based upon the onset date of the AE:

- “Pre-treatment AEs” are AEs with onset dates < date of the first dose of Adagen[®] study medication.
- “Treatment-emergent AEs” are AEs with onset dates \geq date of the first dose of study medication and within 30 days following the date of the last dose of study medication.
- “Post-treatment AEs” are AEs with onset dates > 30 days after the date of the last dose of study medication, within study STP-2279-002.

“Pre-treatment” and “Post-treatment” AEs are considered non-treatment-emergent AEs. For AEs with partially missing onset dates, an onset date is imputed as detailed in Section 12 (Programming Specifications). If an AE has a completely missing onset date, it is

counted as a “treatment-emergent” event, unless the stop date is on or before the date of the first dose of study medication.

If relationship to study drug is missing, for analysis purposes it will be assumed to be related to study drug. For AEs which occur more than once within a time period (see above), the AE which is most related to study drug in that time period will be used in the summary of AEs by categories of relationship to study drug. Similarly, the AE with the maximum intensity in that time period will be used in the summary of AEs by categories of severity.

For each study drug (EZN-2279 or Adagen[®]) medications will be assigned to a time period as follows:

- Medications taken any time < date of the first dose of Adagen[®] during the Lead-in phase will be considered prior medications.
- Medications can be concomitant with either Adagen[®], EZN-2279, or both. Medications taken any time \geq date of the first dose of respective study medication and within 30 days following the date of the last dose of respective study medication will be considered concomitant medications for that study drug.
- Medications taken > 30 days after the date of the last dose of respective study medication will be considered “post treatment” medications for that study drug.

Note that medications can be counted in more than one category (i.e., prior/concomitant) and can have different assignments for different study drugs. Imputation rules for partially missing start/stop dates are described in Section 12 (Programming Specifications).

Change from baseline to Week X in safety endpoints will be calculated as:

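### The SAP's 30-day tail after the last Adagen dose also puts medicines first started on about EZN-2279 Days 1 to 24 into the Adagen concomitant-medication table

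*SAP*

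**What the plan says.** SAP 7.8 plans two descriptive medication summaries: "all medications taken while the patient takes Adagen[®] study drug and all medications taken while the patient takes EZN-2279". Each patient counts once per therapeutic class and once per preferred term.

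SAP 10.6 supplies the window. A medicine is concomitant with a drug if it is taken on or after the first dose of that drug and "within 30 days following the date of the last dose of respective study medication will be considered concomitant medications for that study drug". Nothing closes the Adagen window at the switch. The same section says "Medications can be concomitant with either Adagen[®], EZN-2279, or both". It labels anything taken beyond the 30 days as post-treatment for that drug.

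SAP 10.4 adds a rule for the day of the switch: "Adverse events and concomitant medications starting on the day of the first dose of EZN-2279 are associated with EZN-2279 treatment".

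The interval between the drugs is set in the protocol. Section 11.2.3 says that "the 168 hour post-dose sample will be obtained immediately prior to the initial dose of EZN-2279", and Section 11.3.1 lists the Week T-1 sample as "Trough ADA activity (168 hours following Day 1 Adagen ® PK dose". There is no washout.

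For adverse events, SAP 7.3 gives one summary per drug and limits each to new or worsening events on that therapy.

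**The concern.** A 30-day tail suits a drug that is simply stopped. Here Adagen is replaced by EZN-2279 a week after its last dose, so most of the tail is time on the other drug. A medicine that the patient first takes after the switch then appears in a table that is supposed to describe the Adagen period. The contamination runs one way, because no EZN-2279 time precedes Adagen.

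What is at stake is how the two tables read. Suppose a patient starts an antihistamine on EZN-2279 Day 5 for a new allergic event. Under SAP 7.3 the event appears in the EZN-2279 adverse-event table only. Under SAP 10.6 the antihistamine appears in both medication tables, so a new post-switch medicine can look like one the patient already used on Adagen. The early weeks on a new product are when a reader is most likely to look for such a change.

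**Working it through.** The plan gives no figure for the overlap, so there is none to reproduce. It follows from calendar arithmetic.

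**Inputs**
- Tail after the last dose of the respective drug: 30 days (SAP 10.6).
- Gap from last Adagen dose to first EZN-2279 dose: 168 hours, or 7 days (Protocol 11.2.3 and 11.3.1).
- Dosing tolerance: "EZN-2279 or Adagen® will be administered weekly ± 1 day" (Protocol 10.7.3), so the gap can be 6 to 8 days.
- Minimum Adagen lead-in: 3 weeks, or 21 days (SAP 3.1; Protocol 7.1.1). The documents give no maximum, so longer lead-ins below are assumptions.
- EZN-2279 treatment period: 21 weeks, or 147 days (Protocol 7.1).

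**Last EZN-2279 day inside the Adagen window.** Call the day of the last Adagen dose day 0. EZN-2279 Day *d* falls on day gap + *d* − 1. It lies inside the tail while gap + *d* − 1 ≤ 30, so the last such day is *d* = 31 − gap.
- Gap 7: 31 − 7 = Day 24
- Gap 6: 31 − 6 = Day 25
- Gap 8: 31 − 8 = Day 23

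At the nominal gap, four EZN-2279 doses (Days 1, 8, 15 and 22) fall inside the Adagen window. The overlap is 24/147 = 16% of the EZN-2279 treatment period.

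**Share of the Adagen window that is EZN-2279 time.** Lead-in days run from the first lead-in dose to the day before the first EZN-2279 dose. The share is 24 / (lead-in days + 24).

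| Lead-in | Adagen window (days) | EZN-2279 days in it | Share |
|---|---|---|---|
| 3 weeks (minimum) | 21 + 24 = 45 | 24 | 53% |
| 4 weeks (assumed) | 28 + 24 = 52 | 24 | 46% |
| 8 weeks (assumed) | 56 + 24 = 80 | 24 | 30% |
| 12 weeks (assumed) | 84 + 24 = 108 | 24 | 22% |

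For the minimum lead-in, the doses fall on days −14, −7 and 0. The window from day −14 to day +30 is 14 + 1 + 30 = 45 days, which agrees with the table.

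**Effect on one table row.** Assume six patients, one of whom first takes a given medicine on an EZN-2279 day from 1 to 24, with no use by anyone during the lead-in. A split at the switch shows 0/6 on Adagen and 1/6 on EZN-2279. SAP 10.6 shows 1/6 and 1/6. If that patient already had the same preferred term during the lead-in, the row does not change.

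**After the fix.** Closing the Adagen window at the switch cuts the overlap from 24 days to 0 and, at the minimum lead-in, the window from 45 to 21 days.

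**The case against.** The best case for the present text is that SAP 10.6 openly allows a medicine to count under both drugs, and that its window can be read as the working definition of what SAP 7.8 means by taking a drug. Patients also switch with trough ADA activity of at least 15 μmol/h/mL on Adagen, so the first EZN-2279 days carry some residual Adagen. Dual counting is sensible for a medicine that continues across the switch. It does not explain why one first started after the switch belongs in a table of medicines taken on Adagen. The SAP gives no carry-over argument, and residual activity would not obviously justify 24 days.

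Several stronger readings might be inferred, and the documents do not support them.
- *Post-switch medicines are moved out of the EZN-2279 table.* They are not; they stay there and are added to the Adagen table.
- *The tail biases a within-patient comparison or makes the tables non-comparable.* No comparison of medications is planned. SAP 7.8 is descriptive, and Protocol 13.2.3.5 foresees only a textual description. Exposure is already unequal, at least 3 weeks against 21 weeks or more, and remains so without the tail.
- *About half of the Adagen entries are wrong.* The 53% is a share of calendar days at the shortest lead-in. The documents give no basis for a count of affected medicines.
- *SAP 10.4 is contradicted.* It ties switch-day medicines to EZN-2279 but does not say to EZN-2279 alone.
- *Protocol 12.1 already settles the matter.* It confines the post-Adagen tail to patients who do not switch, "for patients who are withdrawn before switching treatment to EZN-2279, 30 days after the final dose of Adagen", but it concerns adverse-event reporting only. It is a useful parallel, not a rule for medications.
- *A switch reaction would be hidden.* Adverse events are summarized by drug, infections and hospitalizations are summarized for the EZN-2279 treatment period, and SAP 7 lists all safety data.

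**Conclusion.** The point holds as a minor inconsistency. Applied as written, SAP 10.6 puts medicines first started on about EZN-2279 Days 1 to 24 into an Adagen table that SAP 7.8 describes as covering medicines taken on Adagen. It also leaves that table out of step with the adverse-event split in SAP 7.3.

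The 24 days rest on the protocol's 7-day gap and move by one day either way with the dosing tolerance. The shares of 53% and 30% rest on a 3-week and an assumed 8-week lead-in. How many table entries change cannot be stated from the documents; it depends on how many patients start a class or preferred term in those days without having used it during the lead-in.

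Neither the primary nor any secondary endpoint is affected, and neither are the adverse-event tables. The damage is to the reading of one descriptive safety table.

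**What to change.** In SAP 10.6, for patients who receive EZN-2279, end the Adagen concomitant-medication window on the day before the first EZN-2279 dose. Keep the 30-day tail in two places only: after the last Adagen dose in patients who never receive EZN-2279, and after the last EZN-2279 dose.

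Continue to count a medicine that is ongoing across the switch under both drugs. Do not classify medicines taken on EZN-2279 as post-treatment for Adagen. Align SAP 7.8 with the revised window so that the table description and the derivation agree. A separate row for medicines newly started after the first EZN-2279 dose would help a reader but is optional.

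The cost is a short SAP edit and one change to the derivation of the medication period. It needs no new data.

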11. PROGRAMMING SPECIFICATIONS

- All output should have the following header at the upper left margin:

Leadiant Biosciences, Inc.
Study STP-2279-002

And the following header (right-justified) at the upper right margin:

Page X of Y
Report Date: DDMMYY

- Tables and listings should be internally paginated (i.e., page numbers should appear sequentially within each table). All output should have the SAS program name as xxxx.sas in the lower right, and the data source(s) as ADxx used to generate the output in the lower left.
- In general, data listings should be sorted by Patient ID, study drug, and visit/assessment/collection/start dates, unless specific instructions to do otherwise.
- The following algorithm should be used to estimate adverse event start dates for which only partial information is known. To conservatively assign start dates as early as possible first day on study drug is first day of Adagen® study medication.
 - Missing day and month
 - If the year is the same as the year of first day on drug, then the day and month of the start date of drug will be assigned to the missing fields.
 - If the year is prior to the year of first day on drug, then December 31 will be assigned to the missing fields.
 - If the year is after the year of first day on drug, then January 01 will be assigned to the missing fields.
 - Missing month only
 - Treat day as missing and replace both month and day according to the above procedure.
 - Missing day only
 - If the month and year are the same as the year and month of first day on drug, then the start date of drug will be assigned to the missing day.

- If the month and year are before the year and month of first day on drug, then the last day of the month will be assigned to the missing day.
- If the month and year are after the year and month of first day on drug, then the first day of the month will be assigned to the missing day.

If the resultant imputed start date is after the AE stop date (and the AE stop date is complete), the imputed start date will be reset to the AE stop date.

- Adverse events with partially missing stop dates and the “continuing” variable indicated as ‘no’ will have stop dates imputed as follows:
 - *year is missing* – date left missing.
 - *month is missing* – impute ‘December’.
 - *day is missing* – impute ‘last date of that month’.
- Complete dates for concomitant medications with missing or partially missing start dates will be imputed, if necessary, using the same algorithm described for adverse event onset dates. If the stop date is missing or partially missing and the “ongoing” variable is indicated as ‘no’, the imputation rule is applied in the following order:
 - *year is missing* - the medication will be considered to have been received at all periods after that period determined by the start date. Date is left missing.
 - *month is missing* - impute ‘December’.
 - *day is missing* - impute ‘last date of that month’.
- The following algorithm should be used, when necessary, to calculate a start date that is partially missing for medical history:
 - *missing day and month* - January 01 will be assigned to the missing fields.
 - *missing month only* - treat day as missing and replace both month and day according to the above procedure.
 - *missing day only* - assign first of the month to the missing day.
- Partially missing stop dates will be imputed as:
 - *year is missing*, no imputation. Date left missing.

- *month is missing and year is prior to year of first dose of study medication*-impute 'December'.
 - *month is missing and year the same as the year of the first dose of study medication* – impute same month as in start date.
 - *day is missing*: impute 'last date of that month'. If this results in a date \geq the date of the first dose of study medication, impute day as the day prior to the first dose of study medication.
- Date imputations will be applied to the process of assigning study day and should be retained in the analysis datasets, but the data listings should display the original, partially missing dates.
 - Unless otherwise noted (see below), the mean and median (standard deviation and standard error) of a set of values should be printed out to one (two) more decimal place(s) than the raw value.

e.g.,	if raw:	xx
	mean and median:	xx.x
	standard deviation and standard error:	xx.xx
	range (minimum and maximum):	xx, xx

In those cases where the raw data are reported to 2 or 3 decimal places, the mean, median, standard deviation, and standard error will all be displayed to 1 more decimal place than the raw data (e.g., tables summarizing changes from baseline in laboratory parameters).

- All table percentages should be reported to the precision of tenths (i.e., 0.1) unless otherwise noted.
- The following specifications apply to tables that summarize categorical data unless otherwise noted:
 - Percent of events should be left blank (including the parentheses) if the number of events is zero.
 - If the categories of a parameter are ordered, then all categories between the maximum possible category and the minimum category should be included, even if n=0 for a given category between the minimum and maximum level for that parameter.

- If the categories are not ordered, then only those categories for which there is at least one Patient represented should be included.
- A ‘Missing’ category should be added to any parameter for which information is not available for any patients.
- Missing data should be represented on listings as 1) dashes “-”, and properly footnoted: “ - = data not available” or 2) “N/A”, with footnote “N/A” = Not Applicable”, whichever is appropriate.
- Times should be printed in the format “HH:MM”. “HH” represents the 2-digit hour portion of the time. “MM” represents the 2-digit minute portion of the time. Both hour and minute portions of time are zero-filled on the left if they have only one digit. Missing time portions should be represented on patient listings as dashes (“10:--” and “--:--”). Times that are missing because they are not applicable for the patient should be printed as “N/A” unless otherwise specified.
- Adverse event summary tables will only include treatment-emergent AEs. However, listings will include all AEs (i.e., treatment-emergent and non treatment-emergent AEs) with the non treatment-emergent AEs flagged.

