7.3 Adverse Events and Other Complications

All adverse events will be coded using the Medical Dictionary for Regulatory Activities (MedDRA) Version 16.0 or the most recent version prior to database lock. Summaries will be presented for all treatment-emergent adverse events (overall and by severity), adverse events determined by the investigator to be treatment-related (overall and by severity), serious adverse events (SAEs), adverse events causing discontinuation from study, adverse events causing discontinuation from study drug, and non-serious adverse events. In addition to being summarized as adverse events, infectious complications and hospitalizations are considered efficacy measures as are summarized in Section 6.3.

The frequency of adverse events will be summarized using descriptive statistics by system organ class (SOC), preferred term and study drug group. Patients are counted only once in each SOC category, and only once in each preferred term category.

Treatment-related adverse event summaries will include adverse events with missing relationship to study drug. For the summaries by severity, patients are counted at the greatest severity. Adverse events missing the flag indicating serious will be excluded from the summary of serious adverse events but included in the summary of non-serious adverse events.

There will be two treatment emergent adverse event summaries provided: all treatment emergent adverse events while the patient takes Adagen[®] study drug and all treatment emergent adverse events while the patient takes EZN-2279, where treatment emergent are new or worsening adverse events that occur while on the respective therapies.

Listings for all adverse events, deaths, serious adverse events, adverse events leading to discontinuation, MedDRA dictionary terms for adverse event descriptions, and adverse event preferred terms by patient number will be presented.

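### SAP 11 dates partial AE onsets from the first Adagen dose only; on the natural reading some partially dated EZN-2279 events fall in the Adagen table and none move the other way

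*SAP*

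**What the plan says.** - **SAP 7.3** plans two treatment-emergent AE summaries, one per drug, where "treatment emergent are new or worsening adverse events that occur while on the respective therapies". On counting: "Patients are counted only once in each SOC category, and only once in each preferred term category".
- **SAP 10.4** sets the boundary between the drugs: "Adverse events and concomitant medications starting on the day of the first dose of EZN-2279 are associated with EZN-2279 treatment".
- **SAP 10.6** uses the onset date to class an AE as pre-treatment, treatment-emergent or post-treatment. It sends partial onsets to the programming specifications (cited there as Section 12; they are Section 11). A completely missing onset counts as treatment-emergent unless the stop date rules that out, but no drug is named.
- **SAP 11** fixes the reference date: "To conservatively assign start dates as early as possible first day on study drug is first day of" Adagen study medication. With month and day missing in the Adagen start year, "then the day and month of the start date of drug will be assigned to the missing fields"; in a later year, "then January 01 will be assigned to the missing fields". With only the day missing, an onset in the Adagen start month takes the Adagen start date; in a later month, "then the first day of the month will be assigned to the missing day". The one correction begins "If the resultant imputed start date is after the AE stop date (and the AE stop date is complete" and pulls the onset back to the stop date.
- **SAP 11** also keeps imputed dates in the analysis datasets, shows the original partial dates in listings, and reuses the AE algorithm for concomitant-medication start dates.

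**The concern.** The algorithm answers one question, whether an event began on study drug at all, and choosing the earliest possible date is conservative for that question. The per-drug tables ask a second one: which drug the patient was taking. Because the sequence is fixed, an earlier date always favours Adagen as the answer. The rule never compares a partial date with the first EZN-2279 dose, although SAP 10.4 makes that date the boundary.

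At stake is the within-patient AE comparison of the two drugs. With six patients, one patient is 1/6, or 16.7 percentage points, in a preferred-term row. A completely missing onset has a related gap: it is treatment-emergent but has no defined table.

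**Working it through.** The plan states no figure to reproduce, so the check applies the SAP 11 rule as written.

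**Inputs.** The rule and boundary are those of SAP 11 and 10.4. The lead-in is at least 3 weeks and the EZN-2279 treatment period is 21 weeks, or 147 days (protocol 7.1.1). Treatment may last about 2 to 3 years (protocol 7.4.1). Assumptions: Adagen start dates spread evenly over a 365-day year, onsets spread evenly over the EZN-2279 window, and lead-ins of 3, 4, 6 and 8 weeks.

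**Direction.** For an event that began on study drug, the imputed onset is the Adagen start date, the first of the known month, or 1 January of the known year. None of these is later than the true onset, and the stop-date reset only moves a date earlier. An Adagen onset therefore cannot be imputed into the EZN-2279 period: 0% in that direction for every lead-in.

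**Which EZN-2279 events move.**
1. Day missing, onset in the switch month, unless the switch fell on the 1st. (With a lead-in of at least 21 days, a switch on the 1st is always in a month after the Adagen start month.) This spares 12 of 365 start dates.
2. Month and day missing, onset in the Adagen start year or the switch year, unless the switch fell on 1 January. This spares 1 of 365.

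Example A: Adagen starts 20 March and EZN-2279 starts 17 April. An AE on 25 April recorded only as April becomes 1 April and falls under Adagen. Example B: Adagen starts 3 March and EZN-2279 starts 24 March. An AE on 15 July (EZN-2279 Day 114) recorded by year only becomes 3 March and falls under Adagen.

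**Day missing, size.** A switch on day d (d ≥ 2) of a month with m days exposes m − d + 1 EZN-2279 days. Summed over d, that is m(m − 1)/2 per month: 465 for 31 days, 435 for 30 and 378 for 28. The average is (7 × 465 + 4 × 435 + 378)/365 = 5373/365 = 14.72 days per patient, or 14.72/147 = 10.0%. None of these days lies after day 147.

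**Month and day missing, size.** A switch on day d (d ≥ 2) of the year exposes 366 − d days, which takes each value from 1 to 364 once.
- Window of 1 year or more: (364 × 365/2)/365 = 182.0 days.
- 21 weeks (each value capped at 147): (146 × 147/2 + 147 × 218)/365 = 42,777/365 = 117.2 days, or 117.2/147 = 79.7%.

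| EZN-2279 window | Day missing: share moved | Month and day missing: share moved |
|---|---|---|
| 21 weeks | 10.0% | 79.7% |
| 47 weeks | 4.5% | 54.8% |
| 1 year | 4.0% | 49.9% |
| 2 years | 2.0% | 24.9% |
| 3 years | 1.3% | 16.6% |

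The results are the same for all four lead-ins.

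**After the change given below.** No EZN-2279 onset falls under Adagen, but some lead-in onsets go the other way. Without a usable stop date and with a lead-in of L days, min(d − 1, L) Adagen days are exposed, where d is the switch day within the month (day missing) or within the year (month and day missing).
- Day missing: L = 21 gives (7 × 420 + 4 × 399 + 357)/365 = 4893/365 = 13.4 days, which is 63.8% of the lead-in. L = 28 gives 14.65, and L = 42 or 56 gives 14.72.
- Month and day missing: L = 21 gives 7434/365 = 20.4 days (97.0% of the lead-in); L = 56 gives 18,844/365 = 51.6 days.
- Day missing, with a complete stop date 3, 7 or 14 days after onset: 1023/365 = 2.8, 2219/365 = 6.1 and 3850/365 = 10.5 days. With a stop 28 days after onset and a 3-week lead-in there is no reduction (13.4).

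**The case against.** **The drug assignment is inferred.** SAP 10.6 uses the onset date for three periods that do not separate the drugs, and SAP 7.3 does not mention imputed dates. The mock displays are in a separate document. A reader might infer that the SAP directs these events into the Adagen table; it does not say so. What stands is that the tables depend on when an event occurs, imputed dates are kept for analysis, and no other rule is given. Misassignment follows on the natural reading.

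**The affected class may be nearly empty.** Protocol 10.4.4 and 12.3 require the onset date and time. AEs are reviewed weekly and then two-weekly to T-21, and protocol 14.6.2 provides edit checks for missing data. A reader might infer from the 79.7% that most EZN-2279 events would be lost. The documents do not support that: the figure applies only to events with no usable month, and the documents give no count of these. Nor do the 13-week maintenance gaps worsen the day-missing case, because those events move only in the switch month.

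**A moved event may change nothing.** Patients are counted once per term, and the listings show the original dates. The comparison already sets a lead-in of at least 3 weeks against 21 weeks plus maintenance, with no exposure adjustment described. That imbalance is probably larger than this one. The point stands, and it keeps the severity low.

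**Reversing the rule reverses the error.** For day-missing dates without a usable stop date this is correct: 14.7 days now against 13.4 to 14.7 after. The gain there is the direction of error, not its total. This is why the sensitivity table is needed.

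**A careless change would do harm.** Concomitant medications share the algorithm, and SAP 4.1 allows patients who never receive EZN-2279. Both need explicit wording, given below.

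**Conclusion.** The concern holds as a minor defect in a stated rule. If the imputed date selects the table, partially dated EZN-2279 events can only move to Adagen. Over 21 weeks that is 14.7 onset days per patient (10.0%) with the day missing and 117.2 (79.7%) with month and day missing, against zero in the other direction. The percentages rest on evenly spread start and onset dates; the direction does not. No effect on any particular table can be claimed, because the number of partial dates is unknown and probably small.

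**What to change.** For AEs only, and only in patients who received EZN-2279:

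1. **SAP 11.** If the known onset month (or year) ends on or after the first EZN-2279 dose date, and the AE stop date (complete or imputed) is not before that dose, or the AE is continuing or has no stop date, impute onset to the later of the first EZN-2279 dose date and the first day of the known month (or year). Otherwise keep the present rule. Treatment-emergent status does not change.
2. **SAP 10.6.** Assign a completely missing onset to EZN-2279 under the same stop-date condition, otherwise to Adagen. State that AEs in patients who never received EZN-2279 stay under Adagen. Correct the section reference.
3. **SAP 11, concomitant medications.** State that start dates keep the present algorithm with the first Adagen dose as reference, so that medications spanning both drugs stay in both summaries.
4. **Tables.** Add one sensitivity table that counts the ambiguous AEs under Adagen, as the present rule does. Footnote the number of imputed onsets in each per-drug AE table.

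The cost is one programming rule, two clarifying statements, one table and one footnote, with no new data. The downside is that some ambiguous lead-in events move to EZN-2279. For day-missing dates total misassignment falls only with a usable stop date and a short event, to 2.8, 6.1 and 10.5 days for events of 3, 7 and 14 days. For month-and-day-missing dates over 21 weeks it falls from 117.2 days to 20.4 (3-week lead-in) or 51.6 (8-week lead-in), even without a stop date.
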